#### 4.1.4. TMS stimulation and EMG recording

Subjects will be comfortably seated in a dental chair surrounded by a frame that carries a coil holder to assist with the application of TMS to the brain. The MRI of the brain will be reconstructed for neuro-navigation assisted TMS of the brain using Brainsight (Brainsight, Rogue Research, Montreal, Canada). Surface electromyographic (EMG) (bandpass 1 Hz – 1 kHz) activity will be recorded from the target muscle (right and left extensor carpi ulnaris (ECU) and flexor carpi ulnaris (FCU) muscles and other muscles as needed for control), using surface electrodes (11 mm diameter) in a belly-tendon montage and a data acquisition system (LabVIEW, National Instruments, CA, USA). A picture of the subject's arm will be taken to help ensure consistent electrode placement across days. TMS will be applied through an air-cooled figure of eight-shaped coil (7 cm wing diameter) using the rapid Magstim200^2 (Magstim Company, UK). The coil will be positioned on the scalp over the left M1 at the optimal site (hot spot) for stimulating the right ECU. At the optimal site, the resting motor threshold (MT), defined as the minimum stimulus intensity to evoke an MEP of >50  $\mu$ V in at least five

of ten trials (Rossini et al. 1994b), will be determined to the nearest 1% of maximum stimulator output (MSO). The position will be marked on a standard MRI of the brain in Brainsight to ensure coil stability during the experiment.

*Interhemispheric inhibition* : For the measurements of interhemispheric inhibition (IHI) two Magstim 200 stimulators (Magstim Company, UK) will be used. With the subjects at rest, a conditioning pulse (CS) will be applied to the optimal scalp position of the M1 of either hemisphere to stimulate the corresponding contralateral ECU muscle using a figure of eight coil (70 mm diameter) (Ferber et al. 1992). The intensity of CS will be adjusted to produce a MEP of about 1.5 mV (Ferber et al. 1992). A test pulse (TS) will be applied to the homotopic area of the opposite hemisphere, defined as optimal scalp position to stimulate the contralateral ECU using a smaller figure of eight coil (50 mm diameter). The intensity of the TS will be adjusted to produce a MEP of about 1.5 mV (Ferber et al. 1992). Paired pulses at different ISIs will be intermixed with single TS and single CS and applied at random.

*Short interval cortical inhibition*: TMS will be applied through a figure of eight-shaped coil (7 cm wing diameter) using two Magstim 200 stimulators connected via a Bistim module (Magstim Company, UK). Short interval cortical inhibition (SICI) will be measured using paired pulse TMS at an ISI of 2 ms. The intensity of the CS will be varied between 30 and 80% of MT and will be administered randomly (Butefisch et al. 2003; Butefisch et al. 2008) while the intensity of TS will remain suprathreshold. Paired pulses will be intermixed with single test- and conditioning pulses and administered

randomly to M1 of either left or right hemisphere. The sequence of timing of stimuli will be controlled by customized software.

*Active Interhemispheric inhibition:* Active interhemispheric inhibition (aIHI): Active IHI will be measured during the pre- movement time period of a pointing task. In this task subjects have to manipulate a joystick in response to a visual target presented on a computer screen. Real-time feedback about the joystick position is provided by a cursor moving on a computer screen. Subjects will be instructed to move the cursor as quickly as possible to the center of a target square immediately upon its appearance on the screen with a preset time of 2s for movement completion. Feedback (“hit” or “miss”) will be given depending on their ability to move the cursor is in the center of the target within a pre set time of 2 sec. This task was previously reported in detail by our group but modified to allow its manipulation by patients with more impaired hand function and automatic indication of the movement time. This adjustment eliminates the need for selective finger function. For aIHI measures, CS and TS will be applied at the time of the target presentation, 300, 400 or 450 ms after the target presentation at the same ISIs and intensities described for the rIHI.

*Cortical Mapping:* TMS will be applied through a figure of eight-shaped coil (7 cm wing diameter) using the rapid Magstim200^2 (Magstim Company, UK). Motor maps will be derived for the right and left ECU and FCU muscles. A rectangular grid consisting of stimulation sites spaced at least 0.5 cm apart will be superimposed on the subject’s MRI and centered on the subject’s hotspot for a given muscle. EMG activity

and stimulation locations will be recorded as no more than 10 suprathreshold single TMS pulses are applied at each of the stimulation sites. The coordinates of each stimulation site and corresponding EMG activity will be exported for further off-line analysis.

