### 3. Objectives:

**A. Specific Aim #1: *Define key factors that determine the reorganization of contralesional M1 during post stroke recovery process by comparing M1 excitability of stroke patients to that of healthy subjects.*** Our working hypothesis is that the extent of M1 and/or corticospinal tract (CST) damage, as measured by the electromyographic response to TMS of lesioned M1, stroke lesion volume, increased fractional anisotropy (FA) asymmetry of the CST, and quality of wrist/finger extension movements, will determine the extent of contralesional M1 reorganization. In a subset of patients we will also use electroencephalography and TMS to determine the additional key factor of connectivity between the lesioned and the non- lesioned M1 in the post- stroke reorganizational process of contralesional M1.

**B. Specific Aim #2: *Determine the role of contralesional M1 in motor performance during the post stroke recovery process.*** Our working hypothesis is that, during recovery, contralesional M1 contributes to improved motor performance and recovery of the paretic hand in patients with larger M1 and/ or CST damage. Specifically, the extent of M1 and/or CST damage as measured by the electromyographic response to TMS of lesioned M1, lesion volume, increased FA asymmetry of the CST, and quality of wrist/finger extension movements(Nijland et al. 2010) will determine whether contralesional M1 plays a supportive or detrimental role in post-stroke recovery process.

At the completion of this project, we expect to have identified the extent to which

contralesional M1 reorganization determines motor performance during the different phases of post-stroke recovery and can be targeted by interventions depending on its “state” (role) in the recovery process. This latter knowledge would be expected to have a substantial positive impact on treatment for stroke patients as it will provide crucial evidence to develop evidence based TMS treatment protocols that are tailored to the state of therapeutic target. The clinically important question of whether decreasing contralesional M1 activity in patients post stroke is always helpful or at times is detrimental will be addressed.

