amplitude, along with subject type and stimulated hemisphere (as above), will be examined. We will evaluate linear and nonlinear trends of MEP amplitude across intensity levels and will consider various parsimonious parametric structures for the variance-covariance matrix. *For MT*: A mixed model will quantify the effect of subject type (as above) and repeated measure stimulated hemisphere (as above) on MT. *For Mapping*: A mixed model will quantify the effect of subject type (as above) and repeated measure stimulated hemisphere (as above) on the area and CoG of the maps for both ECU and FCU. Furthermore, exploratory analyses and advanced statistical techniques will be used to investigate the relationship between the area and CoG of the maps (i.e., muscle representations at rest) and task-based fMRI activation patterns (i.e., muscle representations during movement).

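### Lesioned-side motor threshold is right-censored at maximum stimulator output but is modelled as if complete, and IHI can be measured only in patients whose lesioned M1 reaches about 1.5 mV

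*Combined protocol and SAP*

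**What the plan says.** **Role of the lesioned-side response.** In section 3, Specific Aim 1 gauges M1 and corticospinal damage partly "as measured by the electromyographic response to TMS of lesioned M1", alongside lesion volume, FA asymmetry and quality of wrist and finger extension. The hypothesis is that this damage "will determine the extent of contralesional M1 reorganization".

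**How the measures are obtained (section 4.1.4).**
- MT is "defined as the minimum stimulus intensity to evoke an MEP of" more than 50 µV in five or more trials out of ten. It is read in whole per cents of the stimulator's maximum.
- For resting IHI, "The intensity of CS will be adjusted to produce a MEP of about 1.5 mV", and for the test pulse on the other side, "The intensity of the TS will be adjusted to produce a MEP of about 1.5 mV". Active IHI is taken "at the same ISIs and intensities described for the rIHI".
- The paired-pulse measure at 2 ms (called SICI here and SICE in section 4.3) uses a conditioning pulse scaled to MT and a test pulse that need only be above threshold.

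**How they are analysed (section 4.3).** All TMS outcomes go into linear mixed models. The MT model uses subject type and "repeated measure stimulated hemisphere (as above) on MT". SICE and IHI are expressed relative to the MEP from the test pulse alone, and IHI is modelled in both directions. The only stated reason for discarding TMS recordings is background EMG activity.

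**Who enters (section 5).** Patients need wrist extension of MRC 3 or better and more than 10 degrees. No MEP is required.

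**The concern.** The plan treats the lesioned-M1 response as a marker of damage, so weak or absent responses are to be expected in some patients and are informative. Yet it has no rule for an MT above maximum output, an absent MEP, or a 1.5 mV target that cannot be reached.

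For MT this affects validity. A patient whose threshold exceeds the maximum has a known fact (the threshold is above the ceiling) but no number. If the cell is left blank, the reason for the blank is the value itself. A likelihood-based mixed model is valid when missingness depends only on observed data, and that condition fails here. Lesioned-side MT would be understated, and with it any elevation relative to controls or to the other hemisphere.

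For SICE and IHI the issue is mainly to whom the result applies. Patients who cannot supply the required MEP drop out of those outcomes, and the report would not show it.

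**Working it through.** The plan states no figure for this, so there is none to reproduce. The check has three steps.

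**1. What each outcome needs from lesioned M1** (sections 4.1.4 and 4.3)

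| Outcome | Needs from lesioned M1 | Lost when |
|---|---|---|
| Lesioned-side MT | MEP above 50 µV in half the trials, within stimulator range | threshold exceeds maximum output |
| Lesioned-side SICE | an MT and a non-zero test MEP | MEP absent |
| IHI, either direction, resting or active | MEP of about 1.5 mV, as conditioning or test response | 1.5 mV cannot be reached |
| Contralesional MT, SICE, SRC, mapping; fMRI | nothing | not lost |

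The two amplitude requirements differ by 1.5 mV / 0.05 mV = 30. A patient with lesioned-side MEPs between 50 µV and 1.5 mV therefore has an MT and can have SICE, but cannot meet the IHI target.

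**2. Size of the MT understatement (illustration)**

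Assumptions, none from the documents: true lesioned-side MT is normal, a share m of patients lies above the ceiling, and those values are left out. On the standardised scale let c satisfy P(Z > c) = m, with φ the normal density.

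- Shift in the mean of the observed values: −φ(c)/(1 − m)
- SD ratio: √[1 − cφ(c)/(1 − m) − (φ(c)/(1 − m))²]

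| m | c | φ(c) | Mean shift (SD) | SD ratio |
|---|---|---|---|---|
| 5% | 1.645 | 0.1031 | −0.109 | 0.900 |
| 10% | 1.282 | 0.1755 | −0.195 | 0.844 |
| 20% | 0.842 | 0.2800 | −0.350 | 0.764 |
| 30% | 0.524 | 0.3477 | −0.497 | 0.702 |

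For example, at 30%: 0.3477/0.70 = 0.497, and √(1 − 0.524 × 0.497 − 0.497²) = 0.70.

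These are shifts in the simple mean of the observed values. A mixed model that also holds the patient's contralesional MT would recover part of the shift, to the extent that the two sides are correlated. It would not recover all of it, because missingness still depends on the unobserved threshold.

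**3. Whether the models use MEP status**

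Section 3 names the lesioned-M1 response as a determinant of contralesional reorganization. The section 4.3 models contain subject type (cortical stroke, subcortical stroke, control), hemisphere or direction, and measure-specific factors such as intensity or interval. None contains the lesioned-M1 response. The one quantity that an MEP-absent patient certainly provides on the lesioned side is therefore missing from the stated models.

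**The case against.** The case on the other side is substantial, and most of it stands.

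- **Small MEPs do not prevent MT or SICE.** Anything above 50 µV gives an MT, and the SICE test pulse need only be suprathreshold. Only IHI is affected by small responses.
- **The plan does not say that patients are dropped.** It is silent, and a mixed model with hemisphere as a factor can keep a patient's contralesional rows when the lesioned-side rows are empty.
- **A reader might infer that the damaged end of the sample disappears from Aim 1 as a whole.** The documents do not support this. The Aim 1 outcome is contralesional M1, and most of its measures need no lesioned-side MEP. An absent response is itself a value of the predictor, and the other three damage measures do not depend on an MEP.
- **A reader might also infer that the damage-reorganization relation is generally attenuated.** That does not follow. Losing one end of a predictor lowers a correlation and costs precision, but does not by itself bias a regression slope, and the plan specifies linear mixed models.
- **The not-at-random argument is confined to MT.** Missing SICE and IHI depend on threshold or MEP size, not directly on the degree of inhibition.
- **The frequency is unknown.** The target muscle is a wrist extensor and entry requires wrist extension, so unmeasurable thresholds may be uncommon.

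What the objection does not answer is that entry requires no MEP, the MT scale has a ceiling, the MT model ignores it, and IHI in both directions depends on a 1.5 mV response from the lesioned side.

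**Conclusion.** The point holds in a limited form. Lesioned-side MT is a right-censored outcome analysed by a model with no provision for censoring, and it will be understated to the extent that thresholds exceed maximum output. The illustrative size is 0.11-0.50 SD for an assumed 5-30% unmeasurable under normality. It concerns the lesioned-side MT mean only, and the true share could be lower. Lesioned-side SICE is a result for patients with an MEP, and IHI in both directions is a result for patients who reach about 1.5 mV; the plan should say so. Contralesional MT, SICE, SRC, mapping and fMRI are untouched, so this is not a claim that Aim 1 as a whole is compromised. It is more than a missing detail, because a censored model and MEP status as a damage level would improve on the stated analysis at little cost.

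**What to change.** 1. Analyse MT with a right-censored (Tobit-type) mixed model, entering thresholds above maximum output as censored at 100% and not as missing.
2. Record lesioned-M1 MEP status for every patient at 1 and 6 months, and enter it as a damage level in the contralesional models that address Aim 1.
3. State that MEP-absent patients stay in all contralesional outcomes.
4. Label lesioned-side SICE as an MEP-present result. Label resting and active IHI as results for patients who reach the 1.5 mV target, which is a narrower group than MEP-present. For each, give the number who could not be measured.

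This is a cheap improvement: one recorded item per visit, standard censored-model software and a few lines in section 4.3. The downside is a distributional assumption for the censored tail.

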#### 4.3. TMS data analysis:

Peak to peak MEP amplitudes will be measured off-line. Recordings with EMG background activity will be excluded from further analysis. Data analysis SICE, SRC, rIHI, aIHI, and mapping: Peak to peak MEP amplitudes will be measured off-line. Recordings with EMG background activity will be excluded from further analysis. For

the SRC, the mean MEP amplitudes at each stimulus intensity will be calculated. For SICE, rIHI and aIHI, mean MEP amplitudes elicited at different ISIs and CS intensities will be calculated as a percentage of the mean test MEP amplitude evoked by TS alone. CS intensities will be expressed as percentage of the subject's MT. For mapping, the area will be calculated as the number of stimulation sites that produce an MEP in of the trials. The center of gravity (CoG), an estimate of the center of the map, will be calculated for each target muscle (ECU or FCU) based on the weighted MEP amplitudes at each active location. Statistical analysis: We will use linear mixed models to quantify the effects of subject type (cortical stroke patient, subcortical stroke patient, healthy control) along with other, measure-specific factors (outlined below) on outcomes of interest. The analyses will incorporate models of within-subject correlations stemming from multiple measures on each subject. Hypothesis testing will be conducted on mean model parameters at a significance level  $\alpha = 0.05$ . Post-hoc analysis will be corrected for multiple comparisons. For SICE: A mixed model will assess the effect of subject type and stimulated hemisphere (ipsi- or contralesional for the stroke subjects, zero for the controls) along with repeated measure CS intensity (60%, 80% MT) on relative conditioned MEP amplitude. For rIHI: A mixed model will be used to determine the dependence of relative conditioned MEP amplitude on subject type along with the repeated measures inhibition (cl\_M1 on il\_M1 and il\_M1 on cl\_M1) and ISI (2ms, 10ms). For aIHI: We will perform a mixed model analysis to determine the dependence of relative conditioned MEP amplitude on subject type along with the repeated measures inhibition (as above), time after go signal (0ms, 300ms, 400ms, and 450ms), and target size (small, extra-large). For SRC: The effect of the repeated measure stimulus intensity on the average MEP

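### Active IHI is probed and modelled at fixed delays after the target, so a patient-control difference at 300 to 450 ms could reflect reaction time; an onset-referenced companion analysis is needed to interpret it.

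*Combined protocol and SAP*

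**What the plan says.** All references are to the combined protocol and SAP.

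- **Intended window** (section 4.1.4, active interhemispheric inhibition): "Active IHI will be measured during the pre- movement time period of a pointing task".
- **Pulse times** (same paragraph): "CS and TS will be applied at the time of the target presentation, 300, 400 or 450 ms after the target presentation". They are not adapted to the subject, hand or visit.
- **Task** (same paragraph): subjects must "move the cursor as quickly as possible to the center of a target square immediately upon its appearance on the screen", with 2 s to complete the movement. The only timing variable named is "automatic indication of the movement time"; reaction time and onset are not mentioned. The paragraph does not say which hand moves during aIHI.
- **Model** (section 4.3): the mixed models estimate the "effects of subject type (cortical stroke patient, subcortical stroke patient, healthy control"). For aIHI the further factors are direction of inhibition, "time after go signal (0ms, 300ms, 400ms, and 450ms), and target size (small, extra-large"). The text does not say whether subject type interacts with time.
- **Trial exclusion** (section 4.3): "Recordings with EMG background activity will be excluded from further analysis".
- **Visits**: section 4 places all measurements at 1 and 6 months. In section 4.4, Study #2, the analyses follow those of Aim 1 with time post-stroke added, but the outcomes then listed are MT, SRC, SICE and rHI. aIHI is not among them.

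**The concern.** The measure is defined by phase of movement, but the pulses and the model's time factor are set by the clock. These agree only if subjects start to move at similar times. Patients are enrolled for hand paresis (section 5), and section 4.1.4 says the task was adapted for more impaired hands, so equal onset times cannot safely be assumed.

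If inhibition changes as movement approaches, a given delay samples a late stage of preparation in a fast group and an earlier stage in a slow one. A systematic shift in onset between groups then enters the subject-type effect and any subject-type-by-time effect. Modelling within-subject correlation does not remove it.

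The background-EMG rule adds a second route. When the probed muscle is in the moving hand, the rule drops trials in which EMG has already begun, and so drops more late-delay trials from the faster group. It does not equalise lead time among the trials that remain.

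At stake is the interpretation of an Aim 1 comparison: a slower reaction could be reported as abnormal interhemispheric inhibition.

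**Working it through.** The plan gives no reaction time, aIHI standard deviation or power figure, so there is nothing to reproduce. **Inputs from the documents:** delays of 0, 300, 400 and 450 ms, alpha 0.05, and 30 healthy controls. Onset times, the inhibition curve, the SDs and a patient group of 30 are assumptions.

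**1. Lead time.** Lead = mean onset − pulse time.

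| Mean onset (assumed) | 300 ms pulse | 400 ms pulse | 450 ms pulse |
|---|---|---|---|
| 400 ms | 100 | 0 | −50 |
| 550 ms | 250 | 150 | 100 |
| 600 ms | 300 | 200 | 150 |

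With onsets of 400 and 550 ms, the controls' 300 ms pulse corresponds to the patients' 450 ms pulse (both 100 ms before onset). The controls' 400 and 450 ms pulses have no patient counterpart.

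**2. Trials with EMG already begun.** Share = Φ((t − mean)/SD).

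- Onset 400 (SD 70): at 400 ms, Φ(0) = 50%; at 450 ms, Φ(50/70) = 76%.
- Onset 550 (SD 110): at 400 ms, Φ(−150/110) = 9%; at 450 ms, Φ(−100/110) = 18%.
- Range at 450 ms: 50% to 95% for onset 450 (SD 80) to 350 (SD 60), against 18% to 6% for onset 550 (SD 110) to 650 (SD 130).
- Later control onset: control 550 (SD 80) gives Φ(−100/80) = 11%, and patient 600 (SD 110) gives Φ(−150/110) = 9%. The selection gap is then negligible.

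**3. Artefact when physiology is identical.** Assume one curve for everyone: the conditioned MEP is 60% of test until 150 ms before onset, then rises linearly to 100% at onset. Onset R is normal and trials with R ≤ t are dropped. The mean of the kept trials is E[curve(R − t) | R > t].

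| Pulse | Onset 500 (SD 60) | Onset 600 (SD 60) | Difference |
|---|---|---|---|
| 0 ms | 60.0 | 60.0 | 0 |
| 300 ms | 61.8 | 60.0 | 1.8 |
| 400 ms | 73.6 | 61.8 | 11.8 |
| 450 ms | 81.4 | 66.1 | 15.3 |

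Averaged over the four delays, the artefact in a subject-type main effect is (0 + 1.8 + 11.8 + 15.3)/4 = 7.2 points. At 450 ms with onset 700 ms the mean is 60.3, which is 21 points below the 500 ms group.

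For the later-control scenario in step 2 (550, SD 80 against 600, SD 110), the same formula at 450 ms gives 72.8 and 67.8, a difference of 5 points. The selection gap has gone but unequal lead time still leaves an artefact.

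**4. Chance that the artefact is declared significant.** With 30 per group and a two-sided test at 0.05, this is about Φ(d/(SD·√(2/30)) − 1.96).

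- d = 15: Φ(15/5.16 − 1.96) = 0.83 at between-subject SD 20, and Φ(15/7.75 − 1.96) = 0.49 at SD 30.
- d = 5: 0.16 at SD 20 and 0.09 at SD 30.

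**The case against.** Several objections have force.

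- **No reaction times are given.** Section 5 documents weakness, not slowness. A reader might infer that the aIHI contrasts are confounded as a matter of fact. The documents support only that they could be.
- **The exclusion gap depends on the assumed onsets.** Section 4.1.4 says the group has reported the task before. If the delays were chosen from that experience, control onsets may be later than 450 ms and few trials would be lost in either group. Step 2 confirms this for the exclusions; step 3 shows that lead time can still differ.
- **Movement contamination is partly handled.** A reader might infer that fast controls contribute data recorded during movement. Where the probed muscle is in the moving hand, the EMG rule removes those recordings. Unequal lead time and trial selection remain.
- **Recovery over time.** A reader might infer that a 1-versus-6-month change in aIHI is equally exposed. That contrast is planned only if the carry-over sentence in section 4.4, Study #2, covers aIHI, and its outcome list does not name it.
- **Go-locked time is a legitimate estimand.** Slow reaction may itself result from abnormal interhemispheric inhibition, and aligning to onset could remove a real difference. This stands: it argues against replacing the planned model, but not against adding a second one.
- **aIHI is one of several mechanistic measures**, and nothing makes it primary. That limits the priority of the point.

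**Conclusion.** The point holds as a limit on interpretation. The pulses and the time factor are locked to the target, and nothing in the documents refers them to onset or adjusts for reaction time. A patient-control difference at 300 to 450 ms therefore cannot, as planned, be separated from a difference in reaction time.

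The size is unknown. Under the assumed curve it is about 15 points at 450 ms for onsets of 500 versus 600 ms and about 5 points for 550 (SD 80) versus 600 (SD 110). It is zero if the onset distributions are equal, and the 0 ms probe is unaffected in every scenario shown. These figures require inhibition to depend on proximity to movement, which the documents do not establish, although sampling several delays suggests that change over preparation is of interest.

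The documents do not support saying that the planned model is invalid or that the bias is present. This is an inexpensive improvement that changes what a group difference can be taken to mean.

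**What to change.** Keep the go-locked aIHI model in section 4.3 and add the following to the SAP.

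1. A prespecified companion model in which clock time is replaced by lead time in ms before EMG onset. Score onset offline from the ECU and FCU recordings, and use the subject's median for that hand, target size and visit (for example from 0 ms trials). Milliseconds are preferable to a percentage of onset time: 82% of onset is 0.18 × 400 = 72 ms before a 400 ms onset, but 0.18 × 550 = 99 ms before a 550 ms onset.
2. A report of onset time and excluded trials by group, delay and visit.
3. An interpretation rule: attribute a group difference at 300 to 450 ms to interhemispheric inhibition only if it persists at matched lead times.
4. Two clarifications: which hand moves during aIHI, and whether aIHI belongs to the 1-versus-6-month analysis.

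**Cost:** SAP wording and offline scoring. The recording window must extend to onset, and its length is not stated. Pulses at 0 ms may themselves shift onset. A subject-level median does not fully correct selection among the retained trials. Late-delay control data, possibly both 400 and 450 ms, may have no matching patient data, as in step 1 of the working.
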